• Examine the referral pathways into MHDUs and the care pathways followed by people before and following an admission to the participating MHDUs, and the extent to which these are influenced by organisational pressures and service users' socio-demographic characteristics and psychiatric history, using electronic patient record (EPR).

Outcomes

• A comprehensive profile of those individuals visiting the MHDU which includes descriptions of the care pathways before and following an admission to the MHDU.

• A model of individual-based factors most relevant to change in key MHDU service user outcomes (e.g., decrease in number of A&E presentations from the period pre-MHDU admission to the period post-MHDU discharge).

Design and Methods

ITS analyses will allow us to assess whether the introduction of MHDUs for people experiencing a mental health crisis accessing emergency care has affected service delivery outcome measures. Service re-design also needs to be examined from a broader context to better understand who is referred to MHDUs (including an equalities 'impact assessment') and what works for which groups of service users and why. A prospective, longitudinal study will address the following research questions:

- 1) How does attending an MHDU impact on psychiatric inpatient admissions and A&E psychiatric episodes/breaches for current MDHU users?
- 2) What are the care pathways before and following an admission to the MHDU for current MDHU users?
- 3) What is the impact of the introduction of MHDUs on inequalities of access to acute mental health services?

Participant selection criteria

All service users at south west London, Lincolnshire, Birmingham, and Sheffield MHDU sites referred for the first time to a MHDU over a 9-month period will be eligible to participate (there are no eligibility criteria other than first admission to MDHU and capacity to consent to participate in research). For sites where service use data cannot be extracted anonymously (e.g. Lincolnshire), only those service users who consent to participation will be included.

Data collection

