Baseline data will be collected for all included participants on socio-demographics (e.g., age, gender, ethnicity, sexuality, postcode) and known predictors of psychiatric admission and health care utilisation by UK adults with mental illness (e.g. diagnosis, previous inpatient admissions, accommodation status, comorbidity, high previous health care utilisation).^{56, 57} In line with previous research, discharge destination after MHDU assessment being admission to psychiatric hospital will be used as a 'proxy of severity' of presentation.⁵⁸ Fields will be specified in pseudonymised Clinical Record Interactive Search (CRIS) reports for those sites with the CRIS facility (SWLSTG and Birmingham), and as appropriate to local Electronic Patient Records system through working with Information Management teams at other sites. The quality and completeness of EPR data is critical to the study. Although data resources including EPR are not shaped by research priorities,⁵⁹ the positive predictive value of EPR has previously been reported as high.⁶⁰ We will test data requirements and identification of fields through repeat iterations as necessary at each site prior to WP3 commencing.

Individual mental health service use data (including those outcomes specified in WP2 in addition to total number of admissions and use of community mental health team (CMHT) and other mental health trust services), numbers of A&E presentations (measured as psychiatric liaison episodes in A&E as recorded in the EPR) and transfers by ambulance and police to MDHU will be collected for each participant for 9 months prior to MHDU admission and 9 months post-discharge. The primary outcome for Mental Health Trust will be the number of informal admissions, and for the acute Trust will be number of A&E presentations.

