Multivariate regression models will be constructed for primary and secondary outcome measures to explore the impact of each predictor variable. It has been proposed that for (multivariate) logistic regression, the minimum number of cases to include is n = 10 k / p, where p is the smallest of the proportions of negative or positive cases in the population and k the number of independent variables.⁶³ For example, if there are (up to) 5 explanatory variables to include in the model and the proportion of positive cases (for key outcomes) in the population is 0.20 (20%), the minimum number of cases required is N=10 x 5 / 0.20 = 250. Throughput for all MHDUs in the study is approximately 30-40 service users per month. We assume informed consent will be obtained for 50% of service users referred to MHDUs in Lincoln and Sheffield, yielding (Lincolnshire = 138; Sheffield = 75). We plan to obtain anonymised data for patients in Birmingham and SWLSTG, (SWLSTG = 270 Birmingham = 668). Participant consent is not required for collection of anonymised data. Including both types of data (collected anonymised data and from consented participants), the anticipated sample size is 1151. These sample sizes will be adjusted in discussion with study sites in relation to actual rates of admission.

Analytical strategy

Initially, the sample of MHDU service user participants will be described with respect to sociodemographics and relevant factors associated with psychiatric admission and health care utilisation (e.g. ethnicity, diagnosis, previous inpatient admissions, accommodation status, comorbidity, previous

health care utilisation).^{56, 57} Where appropriate, individual mental health service use data will be compared between the pre- to post-MHDU discharge periods using paired sample t-tests or McNemar mid-*p* test for binary matched-pair data⁶⁴ depending on distributional properties. Where continuous variables do not meet requirements for univariate normality using skewness and kurtosis estimates, bootstrapping using 2000 replications⁶⁵ will be employed to calculate 95% confidence intervals of mean difference and associated p values.

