In addition to aggregate level data on differences in costs between sites, we will also look at individual longitudinal service user data to determine whether there are sustained significant differences in costs between different MHDU sites and in comparison to at least one control site. Data obtained as part of WP4 will provide information on changes in service utilisation in acute and mental health trusts for individual service users in the 9 months pre- and post-MHDU use or crisis contact (in the case of controls). Appropriate unit costs, such as NHS Reference costs, will then be attached to resources used to estimate incremental changes from an NHS perspective for each specific cost element, as well as total costs of individual service users over the 9 months pre- and post-intervention. Individuals from the control population cohort will be selected to match the characteristics of MHDU service users, allowing us to compare incremental costs between control and MHDU sites (we will select as control site a mental health Trust using the CRIS tool to facilitate generating a control cohort and have begun discussions with a partner Trust to that effect). Where we obtain follow-up data on health-related quality of life from participants we will use that data to model the impact of attending an MDHU on Quality Adjusted Life Years (QALYs). Selected service user sub-group analyses for costs will also be conducted reflecting different socio-demographic characteristics or factors associated with the use of mental health services.

Analytical strategy

Generalised Linear Models (GLMs) and parametric bootstrapping methods will be used to model costs and to determine significance of the differences in individual components of cost, e.g. inpatient length of stay, contacts with CMHTs, use of ambulance services as well as in total costs and, where possible, quality adjusted life years (QALYs).

Decision modelling is an approach that can synthesise existing data on costs and outcomes (in this case changes in the use of acute and mental health trust services) in order to look at potential return on investment of an intervention, such as the introduction of MHDUs. It can be used to deal with issues of uncertainty around effects, levels of uptake and variations in cost, as well as potentially look at the benefits of sustaining change over longer periods of time than can be used in trials and observational studies.

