11. APPENDICIES

11.1 Appendix 1 Research questions

Work Package (WP)	Question	Method	Level	Data source
WP 1 – Review & mapping	1) What is the range of hospital- based, short stay interventions internationally designed to reduce standard admissions to acute psychiatric inpatient care and what is their effectiveness?	Systematic review	Macro	Peer reviewed literature
	2) What is the scope and prevalence of MHDUs nationally and how are they configured?	Service mapping	Macro	Telephone interviews, Mental Health Trust strategic leads
WP2/WP3 – Interrupted time series / Synthetic control study	3a) How has the introduction of MHDUs impacted on psychiatric inpatient admissions and A&E psychiatric episodes/breaches?	Interrupted time series analysis Qualitative interview study	Meso	Routinely collected, aggregate data from Mental Health NHS Trusts and A&E Departments at Hospital NHS Trusts
	3b) What is the impact of policy changes at national level?		Macro	Comparison site time series data Semi-structured interviews with Mental Health Trust and A&E strategic leads and commissioners
WP4 – Cohort study	 3) How has the introduction of MHDUs impacted on psychiatric inpatient admissions and A&E psychiatric episodes/breaches? 4) What are the care pathways before and following an admission to the MHDU? 5) What is the impact of the introduction of MHDUs on inequalities of access to acute mental health services? 	Cohort study	Meso	Routinely collected, individual data of mental health and A&E service use (new admissions to MHDU) Participant characteristics (socio-demographic, psychiatric history etc)
WP5 – Qualitative study	6) How do service users/caters experience MHDUs, as well as crisis care pathways before and after admission to MHDU?	Qualitative	Micro	Semi-structured interviews with service users admitted to MHDU
	7) How are decisions made about referral and admission to MHDU, and assessment and onward signposting & referral?	study		Semi-structured interviews with A&E, Mental Health Trust crisis services and MHDU staff
WP6. Economic analysis	 8) How do the economic costs and impacts of MHDUs compare with areas without MHDUs? 9) How do the costs for individual service users post MHDU implementation compare with their 	Interrupted time series Cohort study	Meso Macro	Economic analysis of aggregate and individual level Mental Health Trust and A&E service use data Appropriate unit cost data attached to services

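### WP4 asks what impact attending an MHDU has, but compares users before and after a crisis without a comparator, so A&E presentations would appear to fall even with no effect

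*Protocol*

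**What the plan says.** Section 5, WP4, Design and Methods lists three questions for the cohort. The first is "How does attending an MHDU impact on psychiatric inpatient admissions and A&E psychiatric episodes/breaches for current MDHU users" and the third is "What is the impact of the introduction of MHDUs on inequalities of access to acute mental health services". Appendix 1 assigns the cohort study the question "How has the introduction of MHDUs impacted on psychiatric inpatient admissions and A&E" together with the pathway and inequality questions. Section 4, by contrast, gives WP4 only pathways and inequalities and places the impact question under WP2/WP3.

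The cohort consists of service users at the four MHDU sites "referred for the first time to a MHDU over a 9-month period will be eligible to participate". Service use "will be collected for each participant for 9 months prior to MHDU admission and 9 months post-discharge". On outcomes: "The primary outcome for Mental Health Trust will be the number of informal admissions, and for the acute Trust will be number of A&E presentations". A&E presentations are counted as liaison psychiatry contacts in A&E logged in the patient record.

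In the WP4 analytical strategy, "individual mental health service use data will be compared between the pre- to post-MHDU discharge periods using paired sample t-tests", with a McNemar mid-p test or a bootstrap as alternatives. Further regressions relate user characteristics to post-discharge use or to the before-after change, again among MHDU users only.

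WP6 plans a matched cohort, with 9 months either side of a crisis contact: "Individuals from the control population cohort will be selected to match the characteristics of MHDU service users, allowing us to compare incremental costs". Its analysis covers cost components, total costs and, where possible, QALYs.

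**The concern.** The question asks for a contrast with what would have happened without the MHDU. The analysis supplies a contrast with the same person's past, split at a crisis. Three features make that past a poor stand-in.

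- **Index A&E contact.** Section 6 names liaison teams, mostly based in A&E, as a referral source. For these users the contact that led to referral precedes MHDU admission and so sits in the earlier window. Nothing matches it afterwards, and the protocol does not exclude it.
- **Entry at a crisis.** Section 6 describes a service aimed at people with heavy use of emergency services. If referral is more likely after a period of high use, counts will drift back down whatever the MHDU does.
- **Direct transfer to a ward.** Section 6 says an MHDU stay is not a formal inpatient admission. A transfer to a ward therefore counts as a new admission after MHDU discharge, in the later window.

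If followed as written, WP4 could report a large, highly significant fall in A&E presentations that owes nothing to the units. The inequalities question has a similar gap: the cohort contains no non-users and no period before the units opened, so it cannot show what their introduction changed.

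**Working it through.** **The plan's own figures.** Minimum N = 10k/p = 10 x 5 / 0.20 = 250. Anticipated N = 138 + 75 + 270 + 668 = 1151. Both reproduce and neither is in dispute.

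**Inputs.** From the protocol: the two 9-month windows, the paired t-test, two-sided 5% significance, N = 1151, and 138 + 75 = 213 from the two consent-based sites. Not in the protocol, so assumed over a range: the share of users p whose index contact was in A&E (25%, 50%, 75%), and the mean number m of other A&E presentations per 9 months (1 or 2).

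**Index event alone, no true effect.** Expected count before = m + p; after = m. Apparent fall = p / (m + p).

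| p | m = 1 | m = 2 |
|---|---|---|
| 0.25 | 0.25/1.25 = 20% | 0.25/2.25 = 11% |
| 0.50 | 0.50/1.50 = 33% | 0.50/2.50 = 20% |
| 0.75 | 0.75/1.75 = 43% | 0.75/2.75 = 27% |

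**Would the test call it significant?** Take the weakest case, p = 0.25 and m = 2. With Poisson counts around a stable personal rate, the variance of the within-person difference is 2m + p(1 - p) = 4 + 0.1875 = 4.1875.

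- N = 1151: SE = sqrt(4.1875/1151) = 0.060; 0.25/0.060 is about 4.1 standard errors; rejection about 99%.
- N = 213: SE = sqrt(4.1875/213) = 0.140; 0.25/0.140 is about 1.8 standard errors; rejection about 43%.

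A gamma-Poisson simulation with no MHDU effect (400 replicates per scenario) agrees: rejection of 99-100% at N = 1151 and 43-100% at N = 213 across the table.

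**Selection on past use alone.** With no index event, but referral probability proportional to 1 + prior count, the simulated false fall was 24% (m = 1) or 16% (m = 2), with rejection of 94-100%.

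**Negative control.** With neither feature, the paired test rejected in 4-7% of replicates. The false signal therefore comes from the index event and the selection, not from the test itself.

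**Informal admissions.** Assuming a mean of 0.4 admissions per 9 months and direct transfer of 10%, 20% or 40% of users, the false change is +0.1, +0.2 or +0.4 per person, with rejection of 95-100%. Regression to the mean pulls the other way and was not included in that calculation, so no net sign follows.

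**With a comparator.** Adding an equally sized matched group entering through the same kind of crisis, and comparing before-after changes, gave an average false effect near zero and rejection of 3-8% (simulation error about 1 point). The simulated controls follow the same process as the users by construction. This shows what a good comparator removes, not that the WP6 controls would be one.

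**The case against.** The strongest reply is that WP4 is mainly descriptive. Its objective and outcomes concern pathways, user profiles and factors associated with change. Section 4 assigns impact to WP2/WP3, the WP4 design text leaves the effect of introducing MHDUs to the ITS, and the paired tests are qualified as used where suitable. This stands, and it is why rewording is an acceptable remedy. It does not remove the point, because WP4 question 1 and Appendix 1 still ask for impact.

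It may also be said that how the index contact is counted is a detail for an analysis plan. But the protocol itself fixes the population, the windows and the before-after comparison.

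Several stronger readings are tempting and are not supported:

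- A reader might infer that the matched controls serve only total costs. WP6 also compares cost components such as length of stay, community team contacts and ambulance use and, where possible, QALYs. What is missing is their use for the two WP4 primary outcomes.
- A reader might infer that the control records are in hand. WP6 says discussions with a partner Trust have begun, so they are planned, not secured.
- A reader might infer that the uncontrolled estimates drive the return-on-investment models. WP6 takes Trust-level changes from WP2/WP3 and plans a controlled comparison for individual costs. WP4 results are said only to inform the scale-up work.
- A reader might infer that admissions are biased upwards, or that direct admissions at the index crisis should be dropped. The sign is unknown. Sections 1 and 2 describe MHDUs as serving people being considered for admission, or who would otherwise have been admitted, so dropping those admissions would discard the very event the unit is meant to avert.

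Finally, WP3 itself warns that parallel trends often fail in health policy settings. That applies to a controlled WP4 analysis too, although the uncontrolled comparison assumes more.

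**Conclusion.** The point holds. WP4 cannot answer its own impact question with the comparison it fixes. For A&E presentations the false fall from the index event alone is about 11-43%, nearly always significant at n = 1151, assuming 25-75% of users enter via A&E and 1-2 other presentations per 9 months. Selection on past use would add to it. The size rests on these assumptions. The index-event bias itself needs only that some users come through A&E liaison and that their referring contact is counted. For informal admissions, direct transfers and regression to the mean act in opposite directions, and the documents do not allow a net direction to be stated. The inequalities impact question likewise cannot be answered from a cohort of MHDU users alone.

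**What to change.** 1. Label the uncontrolled paired comparisons and the before-after change models descriptive. Then either reword WP4 question 1 and the Appendix 1 entry as descriptive and leave impact to WP2/WP3, or analyse the two primary outcomes as a difference in before-after change against the matched controls planned in WP6, if that cohort is secured. The second route should state the parallel-trends assumption and the reliance on as few as one control Trust.
2. Exclude the index A&E presentation from the earlier window, in both groups where controls are used. This is needed on either route, because the change models use the same windows.
3. In the controlled comparison, keep admissions arising at the index crisis, count them from the same crisis-contact time point in both groups, and also report them separately.
4. Use WP4 to describe who reaches the MHDU, and address the inequalities impact question through the gender and ethnicity subgroups already planned for the WP2 ITS.

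The cost is protocol wording, a counting rule and, on the second route, one further model. The second route also brings wider intervals than a paired test and dependence on the control Trust, whose data are not yet secured.

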4 RESEARCH QUESTION/AIM(S)

This is a mixed methods study in six work packages (WPs) addressing the following questions:

Work Package 1: Review and mapping

1) What is the range of hospital-based, short stay interventions internationally designed to reduce standard admissions to acute psychiatric inpatient care and what is their effectiveness?

2) What is the scope and prevalence of MHDUs nationally and how are they configured?

Work Packages 2/3: Quasi-experimental interrupted time series analysis / synthetic control study

3a) How has the introduction of MHDUs impacted on psychiatric inpatient admissions and A&E psychiatric episodes/breaches?

3b) What is the impact of policy changes at national level?

Work Package 4: Quantitative longitudinal study using electronic patient record

4) What are the care pathways before and following an admission to the MHDU?

5) What is the impact of the introduction of MHDUs on inequalities of access to acute mental health services?

Work Package 5: Qualitative longitudinal study

6) How do service users and carers experience MHDUs, as well as crisis care pathways before and after admission to MHDU?

7) How are decisions made about referral and admission to MHDU, and assessment and onward signposting & referral?

Work Package 6: Economic analysis

8) How do the economic costs and impacts of MHDUs compare with areas without MHDUs?

9) How do the costs for individual service users post MHDU implementation compare with their costs prior to the introduction of MHDUs to crisis care pathways, as well as in areas without MHDUs?

10) What are the potential cost impacts of a) alternative configuration of MHDU pathways or access by specific populations, and b) roll out and scale up of MHDUs nationally?

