Formal statistical analysis will include a time series regression analysis, used to estimate the effectiveness of introducing MHDUs on outcome variables. We will adopt an autoregressive integrated moving average (ARIMA) modelling approach,⁴³ as it allows for accurate analysis of outcomes, taking into account any serial correlation, background variation and underlying trends independent of the intervention over time. ARIMA modelling has previously demonstrated successful prediction emergency department (ED) presentations and hospital admission,⁴⁴ including psychiatric visits.⁴⁵

Initially, for each outcome, to check for serial auto-correlation due to repeated measures, we will examine the plot of residuals from regression analyses and use the Durbin-Watson test. Where no significant autocorrelation is detected, we will use a simple time series regression model. If significant autocorrelation exists, then adjustment for autocorrelation will be made using the ARIMA method.

For each outcome, we will calculate regression coefficients corresponding to both change in level (outcome) and trend (slope) after the introduction of MHDUs. In this model, the estimated parameters of interest are as follows: 1 the underlying trend prior to MHDU introduction (b1); 2 the level change immediately following MHDU introduction (b2); 3 the slope change from pre- to post-MHDU introduction

(using the interaction between time and change; b3); 4 the trend (slope change) following MHDU introduction (b1_b3).

Secondary analyses will include separate time series analyses of informal admissions to mental health Trust adult inpatient wards administered considering only people with discharge from psychiatric inpatient services in the last 24 months. In a similar manner, separate analyses of A&E psychiatric presentations will be administered considering only people with a previous A&E visit in the last 24 months. This is to ensure that we can estimate the effect of introducing MDHU on those populations most likely to be repeat users of mental health inpatient care and A&E respectively. External validity will be explored by examination of primary outcomes in subgroups, including but not limited to gender and ethnicity.

Semi-structured interviews; Data collection and interpretation of time series analysis

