Referrals to MHDU can be made from a range of services including liaison psychiatry teams (typically from A&E departments), Crisis Resolution & Home Treatment teams and street triage teams, with referrals triaged at a decision point prior to admission to the MHDU. MHDUs do not accept self- or family referrals, except, by implication, via A&E. Most MHDUs are co-located with a Section 136 Place of Safety, are able to share staff and in some cases, have variable capacity through using flexible partitioning between units. MDHUs have the option of overnight stay – although this often takes the form of reclining seating rather than beds – with maximum length of stay restricted to, typically, 48 or 72 hours (Table 2). Overnight accommodation is single sex, again with flexible partitioning to enable the unit to respond to different numbers of male and female service users. Units tend to be small (capacity of about 6) with staff: service user ratios of at least 1:2 to allow substantial time for detailed assessment, brief intervention and onward referral/ signposting. Brief intervention focussed approaches and so on. Onward referral can be to NHS or third sector services providing therapeutic, social or practical support around, for example, housing, welfare and benefits and so on. MHDUs are typically nurse-led units with

consulting input from psychiatry and other mental health professionals, usually from a co-located acute ward and/ or shared with a Section 136 suite.

MHDU	Max LoS	Accommodation	Capacity	Referral route
South West London	48 hrs	Recliners	5(7 including Section 136 beds)	A&E (liaison), CRHT, Street Triage
Lincolnshire	24 hrs	Recliners	6	A&E (liaison), CRHT

Table 2: Key structural variation in MHDUs at site level

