7.1.1 Inclusion criteria

WP2: Strategic manager interviews

• Strategic managers and Mental Health and Acute NHS Trusts, and mental health commissioners with strategic oversight of MDHUs and the mental health acute care pathway

WP4, WP5: Cohort Study and qualitative interviews with service user participants

- First admission to MDHU
- Capacity to consent to participate in research (for all interviews and for clinical notes' data in sites where service use data cannot be extracted anonymously)

WP5: Staff interviews

- Staff on the referral and assessment pathway to MHDU (including a member of the general hospital based, Liaison Psychiatry team, A&E Nurse and A&E manager at the main general hospital at each site, one or more referring clinician from each of CRHT, street triage service and other agencies that directly refer to MHDU, and a paramedic and police officer involved in transferring people from A&E to MDHU).
- MHDU staff (unit manager, nurse, healthcare assistant and psychiatrist consulting to the unit).

WP5: Carer interviews

• Carer of a service user who has stayed in a mental health decision unit at a site in the DECISION Study.

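### WP4 is asked how introducing MHDUs changed inequalities of access, but a cohort of MHDU users with no crisis-population denominator and no pre-introduction comparison cannot answer that

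*Protocol*

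**What the plan says.** Question 5 in Section 4 reads "What is the impact of the introduction of MHDUs on inequalities of access to acute mental health services" and stands under WP4. Section 5 (WP4, Design and Methods) repeats it as the third WP4 question, and Appendix 1 again lists it against WP4.

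The WP4 population is defined by contact with an MHDU. Section 5 (Participant selection criteria) says that service users "referred for the first time to a MHDU over a 9-month period will be eligible to participate". Section 7.1.1 gives the inclusion criterion as "First admission to MDHU". Appendix 1 gives the data source as "Routinely collected, individual data of mental health and A&E service use (new admissions to MHDU". Section 6 describes MHDUs as working "with referrals triaged at a decision point prior to admission to the MHDU".

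Service-use data are collected for "9 months prior to MHDU admission and 9 months post-discharge". The WP4 analytical strategy describes the sample, compares each person's own service use before and after the stay, and models post-discharge use or change in use.

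Two other places bear on the point. The WP2 analytical strategy states: "External validity will be explored by examination of primary outcomes in subgroups, including but not limited to gender and ethnicity". Question 9, under WP6, asks how individuals' costs after implementation "compare with their costs prior to the introduction of MHDUs to crisis care pathways", and also how they compare with areas without MHDUs.

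**The concern.** The effect of introducing a service on inequality of access is a change over time in a between-group comparison. It needs three things: an outcome that measures access, a denominator of people who might have used acute care, and data from before the service existed. WP4 as specified has none of them. Its *before* period is the time before a person's own MHDU stay, not the time before the unit opened.

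Followed as written, WP4 will deliver the social and ethnic mix of MHDU users, and that mix may be reported as the answer to question 5. Section 2 makes the over-representation of some ethnic groups in coercive crisis care part of the rationale, and the data synthesis plans to identify under-represented groups. A user profile alone supports neither. Question 9 carries the same mislabelling in one of its two limbs.

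**Working it through.** **1. The plan's own figure.** The WP4 site numbers in Section 5 are Lincolnshire 138, Sheffield 75, South West London 270 and Birmingham 668. Sum: 138 + 75 + 270 + 668 = 1151, which matches the stated sample. Every one of these people enters by being referred or admitted to an MHDU.

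**2. What question 5 needs against what WP4 holds.**

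| Needed | WP4 as written |
|---|---|
| Outcome measuring access | Post-discharge service use, or change in a user's own service use |
| Denominator of people in crisis | None named; cohort defined by MHDU referral or admission |
| Comparison with the time before introduction | None; 9 months before the person's own admission |

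**3. What a user profile can show.** Let *s* be a group's share among MHDU users and *π* its share among all people in crisis. The relative odds of access are

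[s / (1 − s)] / [π / (1 − π)].

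WP4 estimates *s* but not *π*. With an assumed *s* = 0.30, s / (1 − s) = 0.4286, and:

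| Assumed π | Relative odds of access |
|---|---|
| 0.10 | 3.86 |
| 0.20 | 1.71 |
| 0.30 | 1.00 |
| 0.40 | 0.64 |
| 0.50 | 0.43 |

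The same observed share fits strong over-representation or strong under-representation. Even with *π* known, this ratio describes access to the unit at one time. A change due to introduction also needs a comparison from before opening. If the later ratio were 1.0, an assumed earlier ratio of 0.5, 1 or 2 would give a change of 1/0.5 = 2.0, 1.0 or 1/2 = 0.5.

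**4. Whether other parts of the protocol supply the missing pieces.**

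- *WP6 control cohort.* WP6 (Data collection) plans controls from at least one non-MHDU Trust, followed around a crisis contact. They are for costs. They are also chosen to match the characteristics of MHDU users, which removes the group differences that an access analysis has to measure.
- *WP2 series.* These cover 24 months before and 24 months after opening, and gender and ethnicity subgroups are planned. They have the pre-opening data WP4 lacks. However, the subgroups are described as a check on external validity, cover the two primary outcomes only, and are not linked to question 5. Compulsory admission is a WP2 secondary outcome, so the planned subgroups do not reach it.

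**5. Question 9.** Its first limb asks about costs before MHDUs were introduced. The individual-level data in WP6 cover the 9 months before and after a person's MHDU use, which is a different contrast. Its second limb, against areas without MHDUs, is served by the control cohort.

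**The case against.** The strongest reply is that the topic is not neglected. WP4 frames part of its work as finding out who is referred, WP5 explores how different groups reach the unit, WP2 already plans ethnicity and gender subgroups on series with pre-opening data, and the synthesis draws these together. Ethnicity and postcode are collected, so an external reference population could be chosen in an analysis plan. All of that is fair. It makes the fault an over-ambitious question placed in the wrong work package, and it means much of the remedy already exists. It does not let WP4 answer the question: eligibility, data source and time window are fixed in the protocol, and an external denominator would still give no comparison with the time before opening.

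A reader might infer four stronger things that the documents do not support.

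- *The study has no non-users.* WP6 plans a control cohort from a non-MHDU Trust.
- *Declined referrals are certainly excluded.* The text conflicts. Section 5 (WP4) and Section 7.3.1 speak of people referred; Section 5 (WP4) and Section 7.1.1 also speak of first admission. If declined referrals were kept, group differences in acceptance could be studied, but not the effect of introduction.
- *No participant's data precede the opening of a unit.* Opening dates are not stated. If WP2 must hold 24 post-opening months by the end of month 18 (31 August 2020), units opened by about 1 September 2018, which is also where a 9-month look-back from month 4 (1 June 2019) begins. That is an inference resting on a tie. If WP2 data ran to 28 February 2021, the latest opening would be about 1 March 2019 and some look-backs could start earlier than opening. They would still come only from people who later reached an MHDU.
- *Question 9 and the return-on-investment work fail.* WP6 already takes the aggregate cost effect of introduction from WP2/WP3 and feeds it to the scale-up model. Only the label on one individual-level comparison is wrong.

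**Conclusion.** The concern holds in this form: question 5 is assigned to a work package whose population, time window and analyses cannot answer it. The gap is one of kind, not degree. All 1151 planned participants are sampled through the MHDU, and in the illustration the same user share is compatible with relative odds of access from 3.86 to 0.43. That range rests on an assumed 30% share and assumed population shares of 10% to 50%; the conclusion does not depend on those values or on when any unit opened.

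In question 9, only the limb about costs before introduction is mislabelled for individual-level data. The comparison with non-MHDU areas stands.

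This should be fixed, but it does not threaten the study's main results. The WP2/WP3 effectiveness analyses are untouched, and WP4 remains a sound source for who uses MHDUs and what happens to them.

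**What to change.** 1. **Answer question 5 from WP2.** Link the gender and ethnicity subgroups already planned to question 5, and add compulsory admissions by broad ethnic group, in line with the Section 2 rationale. State the estimate as the between-group difference in level change and slope change at opening, expressed relative to each group's pre-opening level because groups differ in size.
2. **Narrow WP4's question** to the profile and care pathways of MHDU users, in Section 4, Section 5 and Appendix 1.
3. **Reconcile referral with first admission** as the entry point to WP4 in Section 5 (WP4), Section 7.1.1 and Section 7.3.1.
4. **Reword the first limb of question 9**, for individual-level data, to costs before and after a person's first MHDU admission. Keep the control-site comparison, and keep WP2/WP3 as the source of the aggregate cost effect of introduction.

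The cost is protocol wording plus one further breakdown in a data request that is already being made. Counts by group will be smaller, so broad groups or monthly series may be needed, and precision for a between-group contrast will be lower than for the overall effect. Extracting declined referrals and other crisis contacts at the two CRIS sites would give a denominator for the user profile. It reaches people outside the current WP4 population, would need further approvals, and is optional.
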